12.2.2.3 Big Ten CRC AHQ Requirements for Reporting SAEs to Takeda Oncology

Big Ten CRC AHQ will report SAEs to Takeda Oncology within **1 business day** of receipt of the SAE Reporting Form from a site. Follow-up information will be provided to Takeda Oncology as reasonably requested.

SAE and Pregnancy Reporting Contact Information:

[contact]

Email: [contact]

12.2.2.4 BTCRC AHQ Requirements for Reporting Pregnancy and Birth Events to Takeda Oncology

BTCRC AHQ will report all pregnancy and birth events to Takeda Oncology within **1 business day** of receipt of the Pregnancy Form. Follow-up information will be provided to Takeda Oncology as reasonably requested.

SAE and Pregnancy Reporting Contact Information:

[contact]

Email: [contact]

12.2.2.5 Product Complaints or Medication Errors (Including Overdose)

A product complaint is a verbal, written, or electronic expression that implies dissatisfaction regarding the identity, strength, purity, quality, or stability of a drug product. Individuals who identify a potential product complaint situation should immediately contact Millennium (see below) and report the event. Whenever possible, the associated product should be maintained in accordance with the label instructions pending further guidance from a Millennium Quality representative.

A medication error is a preventable event that involves an identifiable patient and that leads to inappropriate medication use, which may result in patient harm. While overdoses and underdoses constitute medication errors, doses missed inadvertently by a patient do not. Investigators must record all medication errors (including overdose) on the appropriate CRF form. Individuals who identify a potential medication error situation should immediately contact Takeda (see below) and report the event.

For Ixazomib:

Phone: [name] ([name])

E-mail: [contact]

[contact]; **Hours:** Mon-Fri, 9 a.m. – 7 p.m. ET

For TAK-659:

Phone: [name] ([name])
E-mail: [contact]
[contact]; **Hours:** Mon-Fri, 9 a.m. – 7 p.m. ET

Product complaints in and of themselves are not AEs. If a product complaint results in an SAE, an SAE form should be completed and sent to Millennium Pharmacovigilance.

12.2.2.6 Sponsor-Investigator Responsibilities

Big Ten CRC AHQ will send a SAE summary to the sponsor-investigator **within 1 business day** of receipt of SAE Submission Form from a site. The sponsor-investigator will promptly review the SAE summary and assess for expectedness and relatedness.

12.2.2.7 Big Ten CRC AHQ Responsibilities for Reporting SAEs to FDA

For Protocols Conducted Under an IND

Big Ten CRC AHQ has been designated to manage the Investigational New Drug Application (IND) associated with this protocol on behalf of the sponsor-investigator. Big Ten CRC AHQ will cross-reference this submission to Takeda Oncology's parent IND at the time of submission. Additionally, Big Ten CRC AHQ will submit a copy of these documents to Takeda Oncology at the time of submission to FDA.

Big Ten CRC AHQ will be responsible for all communication with the FDA in accordance with 21CFR312 which includes but is not limited to the 7 and 15 Day Reports, as well as an Annual Progress Report. Additionally, Big Ten CRC AHQ will submit a copy of these reports to Takeda Oncology and IU DSMC at the time of submission to FDA.

IND Exempted Protocols

For protocols exempt from the requirements of an IND, the above stated requirements are not applicable. Big Ten CRC AHQ will continue to facilitate compliance of applicable requirements for the sponsor-investigator in relation to this study. This includes but is not limited to 21 CFR 50.20 informed consent, 21 CFR Part 56 IRB, and pertinent sections of the Public Health Service Act and FDAAA.

12.2.2.8 IND Safety Reports Unrelated to this Trial

Takeda Oncology will provide Big Ten CRC AHQ with IND safety reports from external studies that involve the study drug(s) per their guidelines. Big Ten CRC AHQ will forward the safety reports to the sponsor-investigator who will review these reports and determine if revisions are needed to the protocol or consent. Big Ten CRC AHQ will forward these reports to participating sites **within 1 business day** of receiving the sponsor-investigator's review. Based on the sponsor-investigator's review, applicable changes will be made to the protocol and informed consent document (if required). All IND safety reports will also be made available to sites via the EDC system.

Upon receipt from Big Ten CRC AHQ, site investigators (or designees) are responsible for submitting these safety reports to their respective IRBs, as per their IRB policies.

13. STATISTICAL METHODS

13.1 Study Design

Summary tabulations will be presented that will display the number of observations, mean, standard deviation, median, minimum, and maximum for continuous variables, and the number and percentage per category for categorical data.

For the phase I dose escalation study, data analyses will be primarily descriptive and graphical in nature. No formal statistical hypothesis testing will be performed.

For the Phase IIa study, ORR in the response-evaluable population will be estimated with 95% exact binomial confidence intervals (CIs), while considering the adaptive nature of Simon's two-stage design. Time-to-event data will be analyzed by the Kaplan-Meier method and results will be summarized by the 25th, 50th, and 75th percentiles with associated 2-sided 95% CIs, as well as percentage of censored observations, by Flt3WT and mutant populations.

13.2 Sample Size and Accrual

During the dose escalation phase, dose escalation will be conducted according to a standard 3+3 dose escalation schema, and approximately 18 response-evaluable patients will be enrolled. The MTD/RP2D cohort will have at least 6 patients.

The sample sizes for the Phase II study are estimated using a one-sided test at a significance level of $\alpha=0.1$ with power of 80%. To perform the phase 2 study, we will consider a Simon's stage 2 design (See Study Overview Diagram) (39, 40). The primary objective of the phase 2 portion of the study is to detect an efficacy signal that warrants further development of the combination in AML, which will likely be annotated by molecular genetic mutational subgroups. It is most likely those will exist within the rubric of Flt3 mutation. The primary measure of efficacy for the phase 2 portion will be ORR, which will include CR, CRp, CRI, and PR. Best response will be assessed by the end of Cycle 3 of TAK-659/Ixazomib combination for the purpose of an interim analysis between Stage 1 and Stage 2. The Flt3WT and Flt3mut cohorts will proceed to the second stage if patients respond by CR, CRp, CRI.

It has been established in other trials involving single-agent Flt3-selective inhibitor(s), such as FDA-approved Gilteritinib, that a composite complete response rate of approximately 40% occurs in AML patients with Flt3 mutations (41). **However, in cases of subclonal mutant Flt3 allele burden, this may not occur, especially because the epigenetic co-mutation driver is not addressed by the TKI.** In such cases, we will stratify response rates of Flt3 mutant cohorts by mutFlt3 Variant Allele Frequency (VAF) in order to address the possibility that the proteasome inhibitor Ixazomib may contribute to clonal reductions of the clones bearing epigenetic comutational driver allele as well as a subclonal mutFlt3 population, or those that lack the mutant Flt3 allele altogether. However, despite this advantage, we would not accept markedly inferior response rates overall should they indicate a response rate less than expected for active single agent Flt3 inhibitor, and therefore set the futility threshold below 30%.

Therefore, within the Simon's two-stage design, the Flt3 mutant cohort uses as null hypothesis of response rate $\leq 30\%$, versus an alternative hypothesis of response rate $\geq 55\%$. Based on a Simon 2-stage Optimal design, 8 patients will be accrued in the first stage. If there are 2 or fewer responses in the 8

patients, the study will be stopped. Otherwise, 12 additional patients will be accrued for a total of 20. The treatment will be recommended for further study if 8 or more responses are observed in 20 patients.

On the other hand, we will follow the above rationale that proteasome inhibitor Ixazomib may contribute specific targeting of the epigenetic co-mutation driver allele in order to enhance what has been a limited contribution to antileukemic efficacy of Flt3-selective TKI's, such as Gilteritinib, as observed within subclonal Flt3 mutant as well as Flt3wild-type disease cohorts (42; see de Boer B, et al. *Cancer Cell*.2018;34:674-689). Indeed, the phase I/II trial for Gilteritinib reported an 8% (average of 120mg and 200 mg dose cohorts) composite Complete Response rate (CRc), and an average 16% ORR for Flt3wild-type disease which was vastly inferior to Flt3 mutant (AE Perl, et al. *Lancet Oncology* 18: 1061, 2017 [ref 41][see Table S8]).

Thus, there is a great need to establish platforms to target the **epigenetic co-mutation drivers of the Wnt/β-catenin pathway to HoxA, such as TET2 and WT1, as well as DNMT3A, EZH2 and ASXL1, where our in vitro evidence obtained on mutationally annotated Flt3 wild-type disease demonstrates promising activity of the combination of TAK-659 and Ixazomib.** Indeed, Syk inhibition, not simply Flt3 inhibition by the dual Flt3/Syk inhibitor appears to play an important role in such settings. Further, we have evidence that not only does TAK-659's Syk inhibitory activity target resistance mechanisms in Flt3 mutant AML, but that in combination with Ixazomib, there exists unique efficacy within the Flt3 wild-type AML's arising from the above effectors.

We will employ an initial comparator for targeted therapy futility of the combination in Flt3-WT patients, using a threshold response level similar to that derived from recent phase III trials among all-comers of Intermediate-dose cytarabine (IDAC) in different combinations, where the composite complete response (CRc) [CR, CRi, CRp] was approximately 21% among all-comers ([43,44]Roboz et al. *JCO* 2014, Faderl et al. *JCO* 2012) However, other studies find a much lower aggregate response rate equal or less than 12% by supplementation of the IDAC backbone with either gemtuzumab, liposomal daunorubicin, or by cytoxin/topotecan ([45]Litzow, et al. *BrJ Haem.* 2010). Thus, the initial futility screen for the Flt3WT cohort uses a null hypothesis response rate of $\leq 15\%$ versus an alternative hypothesis of response rate $\geq 40\%$. Based on a Simon 2-stage Minimax design, approximately 9 patients will be accrued in the first stage. If there are 1 or fewer responses in the 9 patients, the study will be stopped. Otherwise, 7 additional patients will be accrued for a total of 16. The treatment will be recommended for further study if 5 or more responses are observed in 16 patients.

In addition, our broader goal is to later compare in exploratory fashion, the response rate among the subjects whose epigenetic mutational profile fits that profile of driver mutations acting in the Wnt-β-catenin pathway, which our combination is designed to target, to the **“investigator choice”** standard for all-comers noted above. We propose to assign a response rate among our sensitive population with the epigenetically-active mutant drivers noted above, in an attempt to validate the sensitivity paradigm we have enunciated from our in vitro testing of NGS-annotated primary blasts. Indeed, we are testing the combination whose activity links with a mutational complement of epigenetic effectors for which no targeted therapy currently exists (epigenetic co-mutation drivers of the Wnt/β-catenin pathway to HOXA, such as TET2 and WT1, as well as DNMT3A, EZH2 and ASXL1), where our in vitro evidence

obtained on mutationally annotated Flt3 wild-type disease demonstrates promising activity of the combination of TAK-659 and Ixazomib.

Other efficacy measures, such as DOR, TTP, ability of the therapy to provide bridge to transplant, and mortality rate will also be considered in the decision to expand the study. Best responses from both cohorts will be assessed individually and combined in an effort to understand the all-comer response rate. Upon enrollment, the mutational profiles from Foundation One, Mayo, Tempus, Quest, ARUP, or an institutional CLIA-certified laboratory will be recorded in the database with minimum gene coverage as noted in Section 8.3.

Retrospective analysis will be performed to identify additional patient selection markers beyond mutational profile, by scrutiny of the expression levels of mRNAs for target drivers in context of epigenetic repression of tumor suppressor genes noted in our prior published study. Particular emphasis will be paid to the reversal of a signature for hyperexpression of HOXA9/10 and MEIS1 in a final common pathway for treatment resistance that will have been reversed by upmodulation of the repressed tumor suppressors RUNX3 and/or DAPK1, while strongly dampening the agonists for β -catenin ID1, JUN, and FOXM1.

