--	--

[figure not shown]
	
the first stage. If there are 1 or fewer responses in the 9 patients, the study will be stopped. Otherwise, 7 additional patients will be accrued for a total of 16. The treatment will be recommended for further study if 5 or more responses are observed in 16 patients. The Flt3 mutant cohort uses a null hypothesis of response rate $\leq 30\%$, versus an alternative hypothesis of response rate $\geq 55\%$. Based on a Simon 2-stage Optimal design, 8 patients will be accrued in the first stage. If there are 2 or fewer responses in the 8 patients, the study will be stopped. Otherwise, 12 additional patients will be accrued for a total of 20. The treatment will be recommended for further study if 8 or more responses are observed in 20 patients. Other efficacy measures, such as DOR, TTP, ability of the therapy to provide bridge to transplant, and mortality rate will also be considered in the decision to expand the study. Best responses from both cohorts will be assessed individually and combined in an effort to understand the all-comer response rate.
 
Retrospective analysis will be performed to identify potential patient selection markers for response, including the expressions of Syk, and the Wnt pathway agonists (ID1, JUN, FOXM1, β-catenin) and antagonist RUNX3, and the end-targets expected of TAK-659 and Ixazomib, HOXA and MEIS1, when measured before and then sampled early into therapy. Interpretation of these measures will be made in context of mutational profile of cooperating epigenetic mutations, especially involving TET2, IDH2/1, WT1, as well as DNMT3A, without or with Flt3 mutation, available by next-generation sequencing of patient marrow samples.

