5.3.1 Number of treatment cycles

Given our experience with this sort of treatment algorithm, we will follow the cues previously established in the Sorafenib/Vorinostat/Bortezomib trial to determine the course.

We will follow the peripheral blood blast reduction during the first cycle of therapy. When peripheral blasts have been reduced by at least 50%, we will perform a bone marrow, either day 4 or 8, to document if similar effects are occurring in the marrow as in the periphery. Also, excess cells obtained from the marrow at this early time point will be used to inform the impact of changes in gene signature from baseline marrow, which will have been obtained on the registration/pretreatment visit at day -4 to 0.

Usual supportive care transfusions will occur during the treatment cycle to maintain platelet count >10k at weekly assessments, and hematopoietic growth factors are not mandated as long as ANC >200/uL. Treatment outcome assessment will involve a bone marrow performed at day 15.

Assuming achievement of 50% or greater reduction in marrow blast score (cellularity x blast percentage) after 2 cycles, another cycle will be given. If the patient has had a response (CR, CRp or CRi) after 2 cycles, every attempt will be made to transition the patient to transplant.

However, if the patient is not a transplant candidate but the response after 2 cycles reaches the threshold 50% reduction, continuation of therapy cycles can continue with follow up bone marrow after the next 2 cycles as long as no evidence of peripheral progression occurs. Evidence for progression in the bone marrow would be a cue for discontinuation of therapy.

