8.5 Phase II Interim Analysis

An interim analysis for futility stopping will be conducted to determine whether continuation of the Phase II study is warranted. The investigator-assessed response rate will be used as the endpoint for the interim analysis. The FLT-3 mutant and FLT-3 WT cohorts will be evaluated independently and could be subject to enrollment hold by individual cohort.

For the FLT-3 mutant cohort, the interim analysis will be performed when the first 8 response-evaluable patients have completed 3 cycles of therapy or have discontinued therapy before 3 cycles. If more than 2 responders are observed out of these initial 8 evaluable patients, patient enrollment will continue. The number of evaluable patients needed in the second stage is 12.

For the FLT-3 WT cohort, the interim analysis will be performed when the first 9 response-evaluable patients have had the opportunity to complete up to 3 cycles of therapy or have discontinued therapy before 3 cycles. If more than 1 responder is observed out of these initial 9 evaluable patients, patient enrollment will continue. The number of evaluable patients needed in the second stage is 7. These parameters were developed in context of the Statistical Methods described in Section 13.

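### The readable plan does not say whether a partial response counts at the stage 1 decision, or whether p0/p1 are ORR or composite-CR rates, so the same stage 1 data can stop or continue a cohort

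*Combined protocol and SAP*

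**What the plan says.** - **Primary endpoint.** Section 13.2: "The primary measure of efficacy for the phase 2 portion will be ORR, which will include CR, CRp, CRI, and PR". Sections 2.2.1 and 13.7.1 also count PR in ORR.
- **Moving to stage 2.** The same paragraph of 13.2, repeated in two places in the Synopsis, says "The Flt3WT and Flt3mut cohorts will proceed to the second stage if patients respond by CR, CRp, CRI". PR is not listed and no number is attached.
- **Numeric stops.** For the wild-type cohort (Synopsis and 13.2): "If there are 1 or fewer responses in the 9 patients, the study will be stopped". For the mutant cohort: "If there are 2 or fewer responses in the 8". Neither says which response categories count.
- **Section 8.5.** "If more than 1 responder is observed out of these initial 9 evaluable patients, patient enrollment will continue", and for the mutant cohort "If more than 2 responders are observed out of these initial 8 evaluable patients, patient enrollment will continue". Responder is not defined there; the section ends "These parameters were developed in context of the Statistical Methods described in Section 13", which sends the reader back to 13.2.
- **Hypotheses.** 15% against 40% (wild-type) and 30% against 55% (mutant), labelled only as response rates. The benchmarks in 13.2 are on mixed scales: composite CR of about 40% for mutant disease, composite CR of about 21% for all-comers, an aggregate response rate of 12% or less, and, for another drug in wild-type disease, composite CR of 8% beside ORR of 16%.

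The Study Overview Diagram that 13.2 cites for the design is not shown in the text available for this review.

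**The concern.** This is the efficacy go/no-go decision for each cohort, taken after 8 or 9 patients, where one patient can decide it. If the counted event is not fixed, two teams can each follow the written plan and decide differently on the same data, and the reading can be chosen once the responses are known. The printed cutoffs also come from a design with one event and one pair of rates. If stage 1 counts one event and the final analysis another, or if p0/p1 are on a different scale from the count, the stated 80% power and 0.10 type I error are no longer assured.

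**Working it through.** **Opposite decisions (no assumption needed).**

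| Stage 1 data | CR-type count | ORR count |
|---|---|---|
| Wild-type: 1 CRi + 1 PR of 9 | 1, stop | 2, continue |
| Mutant: 2 CR + 1 PR of 8 | 2, stop | 3, continue |

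**Inputs from 13.2.** Wild-type: n1 = 9, stop at r1 = 1 or fewer, n2 = 7, success at R = 5 or more of 16. Mutant: n1 = 8, r1 = 2, n2 = 12, R = 8 or more of 20. **Assumption:** s, the share of ORR responders whose best response is PR, independent across patients. The plan gives no value, so 5%, 10% and 20% are shown.

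**Step 1: reproduce the plan with one definition throughout.** With x the stage 1 count:

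P(success) = Σ over x > r1 of b(x; n1, p) × P[Bin(n2, p) ≥ R − x].

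Wild-type at p = 0.40, terms x = 2, 3, 4 and 5 or more: 0.0935 + 0.2110 + 0.2438 + 0.2666 = 0.8149. At p = 0.15 the same sum is 0.074. The wild-type design therefore meets 80% power and 0.10 when one definition is used. Mutant: power 0.881, type I error 0.185; the excess over 0.10 comes from the final cutoff and is a separate issue.

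**Step 2: CR-type count at stage 1, ORR at the end, p0/p1 as ORR.** Each term is weighted by the chance that enough of the x responders are CR-type:

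P(success) = Σ over x of b(x; n1, p) × P[Bin(x, 1 − s) > r1] × P[Bin(n2, p) ≥ R − x].

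Wild-type at s = 0.20: the weight is 0.8² = 0.64 for x = 2, 0.896 for x = 3, 0.973 for x = 4 and close to 1 above that. The terms become 0.060 + 0.189 + 0.237 + 0.265 = 0.751.

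| PR share | Wild-type power | Mutant power |
|---|---|---|
| 0 | 0.815 | 0.881 |
| 5% | 0.804 | 0.855 |
| 10% | 0.790 | 0.824 |
| 20% | 0.751 | 0.743 |

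Power falls below 80% above a share of about 6.6% (wild-type) or 13% (mutant). Type I error falls as well (wild-type 0.064 at 20%).

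**Step 3: how often the two stage 1 counts disagree, at the alternative.**

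P(disagree) = P[Bin(n1, p(1 − s)) ≤ r1] − P[Bin(n1, p) ≤ r1].

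At s = 0.20, wild-type: P[Bin(9, 0.32) ≤ 1] − P[Bin(9, 0.40) ≤ 1] = 0.163 − 0.071 = 0.092. Mutant: P[Bin(8, 0.44) ≤ 2] − P[Bin(8, 0.55) ≤ 2] = 0.2376 − 0.0885 = 0.149. At 5/10/20% the results are 1.8/3.9/9.2% (wild-type) and 2.9/6.3/14.9% (mutant).

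**Step 4: same mixed rule, p0/p1 as composite-CR rates.** The ORR is then p0/(1 − s) under the null; at s = 0.20, wild-type, 0.15/0.80 = 0.1875. Wild-type type I error is 0.086/0.100/0.135 at 5/10/20%, passing 0.10 at a share of about 10%. Power is not lost (0.908 at 20%).

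**The case against.** **The plan does state a rule.** The CR-type sentence appears three times in the same words, and 8.3 times the Cycle 3 marrow to document composite CR. A strict early futility rule with a broader final endpoint is a legitimate design. This has weight. Even so, the numeric stops and 8.5 leave the counted event undefined, the sentence itself carries no count, and no operating characteristics are given for a mixed rule. Reading it as at least one CR-type response is possible but strained, because numeric stops follow; it would cost little power (wild-type 0.823 at a 20% share if it replaced the count, 0.809 if added to it).

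**Other sections point to ORR.** Sections 2.2.1 and 13.7.1 include PR, and the phase I efficacy criteria in 5.3 are set as ORR. That supports an ORR scale for p0/p1 but does not bind the stage 1 count. Conversely, the wording in 5.3.1, "If the patient has had a response (CR, CRp or CRi) after 2 cycles", concerns transition to transplant, and the PR/nonresponse grouping in 13.8 is an exploratory tabulation. Neither defines the count in the two-stage design.

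**PRs may be rare.** Section 8.2 requires CR-level blood counts for a PR, and 1.4.5 lists three responders on single-agent TAK-659 (one CR, two CRi) and no PR. This stands: at a 5% share both cohorts keep 80% power and the two counts rarely disagree. Three responders cannot establish the share for the combination, however.

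**The missing diagram.** It may label the counts, so the point is limited to the text that can be read.

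**Conclusion.** The concern holds in a limited form: the readable text does not reconcile the sentence on proceeding with the ORR definition, and it does not state the scale of p0/p1. The opposite decisions in the two examples need no assumption. The change in power or type I error does: it rests on an assumed PR share, on independence across patients, and on which scale p0/p1 are given. It is small at 5% and material by 20%.

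A reader might infer three stronger things that the documents do not support.

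- That any mismatch of definitions breaks the stated error rates. It does not: wild-type under the mixed rule on the ORR scale at a 5% share still has power 0.804 and type I error 0.072, while the mutant cohort misses 0.10 even with matching definitions.
- That half of responders will be PRs, from the 8% and 16% quoted for another drug. Those figures concern a different agent, and the ORR definition behind them is not given, so they cannot be carried over.
- That the mutant type I error of 0.185 is caused by this ambiguity. It comes from the cutoff of 8 or more of 20 and is present under any single definition.

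**What to change.** Before stage 1 data are seen, write one response definition for both the stage 1 count and the final count into the Synopsis (Study Design and Statistical Considerations), 8.5, 13.2 and 13.7.1. State there whether p0/p1 are ORR or composite-CR rates, and check that the Study Overview Diagram agrees.

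**Default:** ORR (CR, CRp, CRi, PR) at both stages, p0/p1 declared as ORR rates, composite CR reported alongside. This matches the primary endpoint, keeps the printed sample sizes and stage 1 cutoffs, and gives wild-type power 0.815 and type I error 0.074. Because the mutant benchmark is a composite-CR rate, add a sentence saying why 30% is the right ORR null.

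**Cost:** this is more than a wording change, because it replaces the CR-type sentence on proceeding. Stage 2 then opens more often. At a 20% PR share and the null ORR, opening rises from 1 − 0.705 = 30% to 1 − 0.599 = 40% (wild-type) and from 1 − 0.703 = 30% to 1 − 0.552 = 45% (mutant). Declaring the scale also matters: if p0/p1 are really composite-CR rates, ORR at both stages gives wild-type type I error 0.157 at a 20% share, above the mixed rule's 0.135.

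**If a CR-type rule at stage 1 is intended:** say so, give its count, say how it relates to the 1-of-9 and 2-of-8 stops, and report joint power and type I error over a range of PR shares. If composite CR is meant throughout, state the hypotheses on that scale; wild-type then keeps 0.815 and 0.074 at any PR share, but the primary endpoint changes.

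The mutant final cutoff needs its own correction.

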8.3 Bone Marrow Biopsy and Aspirate Collection Analysis

If prior results are not available, bone marrow biopsy and aspirate collection at screening will be required to assess disease burden, and exclusively from aspirate: cytogenetics, karyotype, mutations by NGS and Flt3 mutations by quantitative PCR and cellular composition by flow cytometry. Both of these tests should be done by CLIA- and/or FDA-approved vendors as standard of care. In the case of NGS testing, preference would be to have results obtained from Foundation One, Mayo, Tempus, Quest, ARUP or an institutional CLIA-certified laboratory, rendering results for a least 27 AML/MDS driver genes. If bone marrow aspiration has failed, a peripheral blood sample with circulating blasts may be substituted.

A minimum 27 gene mutational profile standard in practice for tracking mechanism and prognosis (1,3):

AML Mutations by NGS (ASXL1, CEBPA, DNMT3A, ETV6/TEL, FLT3, HRAS, IDH1, IDH2, KIT, KRAS, MLL, NPM1, NRAS, PHF6, RUNX1, TET2, TP53, WT1)

MDS Mutations by NGS (ASXL1, ATRX, BCOR, BCORL1, ETV6/TEL, DNMT3A, EZH2, GNAS, IDH1, IDH2, RUNX1, SF3B1, SRSF2, TET2, TP53, U2AF1, ZRSR2).

MPN Mutations by NGS (ASXL1, BRAF, CALR, CSF3R, EZH2, IKZF1, JAK2, JAK3, KDM6A, KIT, MPL, PDFGRA, SETBP1, TET2)

(the latter two panels have certain targets that apply more commonly to secondary AMLs)

Additional bone marrow aspirates (remaining aspirate material from the first pull or a second or third pull of bone marrow aspirate) and biopsy specimens (segments of the first core biopsy or additional core biopsies) will also be required at screening and during the study for biomarker analysis.

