13.8 Exploratory Objectives and Pharmacokinetic Analysis

The data analyses for these exploratory objectives are mainly descriptive. We will begin such analyses by tabulating the pairwise combinations of class1/class2 mutations that occur within the Flt3- mutant vs. -wild type cohorts and summarize the frequency of these mutations (most frequent class 1 are Flt3mutation (both ITD and TKD) ~40%; vs. N/KRAS 20%); within class 2 (NPM1 40%, IDH2/IDH1 ~20%, TET2 ~15%, WT1 ~10%, ASXL1 15%). CR/CRp vs PR/nonresponse rates will be tabulated among groups based on presence of combinational number (combinational burden) and type, and will be compared by Fisher's exact test. ORR will be summarized with 95%CI and PFS will be analyzed by Kaplan-Meier methods in the whole study population and in the subgroups defined by the mutation subtypes. Additionally, we will explore the noted response groups based on identified markers from our prior trial that were predictive of ability to achieve or not remission, including ID1, JUN, HOXA, as well as the currently added markers- β -catenin and FOXM1, examining their individual association with remission status using logistic regression model.

The plasma concentrations of TAK-659 will be determined by validated liquid chromatography tandem mass spectrometry (LC/MS/MS) assay methods. The pharmacokinetic population will be those patients whom have at least one measurable post TAK-659 dose concentration. Plasma TAK-659 concentrations will be summarized by time postdose, grouped by dosing schedule, dose group, and dosing cycle and day. Mean and individual plasma TAK-659 concentration data will be plotted over time, grouped by dosing schedule, dose group, and dosing cycle and day.

Sparse Plasma PK data from Phase I and Phase II will be used for the estimation of PK parameters in the PK-Evaluable Population, as noted in the prior section. Dose proportionality of TAK-659 plasma exposures will be evaluated by visual inspection of plots of individual PK parameter values versus dose. If data permits, regression analysis using a power model will also be used to assess dose proportionality.

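### FLT3-mutant response is to be examined by VAF strata alone, in at most 20 patients and with no cut stated; baseline VAF should also be analysed on its full scale as an exploratory analysis

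*Combined protocol and SAP*

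**What the plan says.** Section 13.2 notes a composite complete response rate of about 40% with single-agent FLT3 inhibitors in FLT3-mutant AML, then cautions that "in cases of subclonal mutant Flt3 allele burden, this may not occur". Its answer is that "we will stratify response rates of Flt3 mutant cohorts by mutFlt3 Variant Allele Frequency (VAF"), to address the possibility that ixazomib acts on clones the kinase inhibitor misses. Subclonal is not defined numerically, and no number of strata, test or significance level is attached.

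The cohort is small: 8 patients in stage 1, then "12 additional patients will be accrued for a total of 20". The design parameters, a "one-sided test at a significance level of $\alpha=0.1$ with power of 80" per cent, belong to the Simon test of ORR and not to any VAF comparison.

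VAF is measurable. Section 8.3 lists "mutations by NGS and Flt3 mutations by quantitative PCR" at screening, and Section 9 plans digital PCR of driver-gene allele frequency.

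Section 13.8 names Fisher's exact test for groups defined by mutation combinations. For ID1, JUN, HOXA, β-catenin and FOXM1 it plans "examining their individual association with remission status using logistic regression model". VAF appears under neither method. Section 13.7.1 says phase II is not meant to demonstrate outcome differences among disease groups, and Section 13.8 calls the exploratory analyses mainly descriptive.

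**The concern.** The plan takes a variable measured on a continuous scale and commits only to a grouped summary of it. If response rises steadily with VAF, grouping treats every patient on one side of the cut as alike and discards the ordering within each group. In a large trial this matters little. With 20 patients split in two, each stratum holds about 10, and with 8 patients about 4.

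The missing cut is a second weakness. A boundary for subclonal disease picked after responses are known can be placed where it separates responders best, which biases the comparison. The patient examples in Section 1.3 run from 2% through 14% to over 50% allele burden and suggest no natural threshold.

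What is at stake is the quality of an exploratory answer that Section 13.2 specifically promises. The primary ORR test is not affected.

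**Working it through.** **The plan's own figure.** The documents give no power figure for VAF, so the figure to reproduce is the cohort size, 8 + 12 = 20. An exact binomial search for the Simon optimal design at 30% versus 55%, alpha 0.10 and power 80%, returns 8 patients in stage 1 (stop at 2 or fewer responses) and 20 in total. The size reproduces. (The same search puts the success boundary at 9 of 20, not 8; that is a separate matter and nothing below uses it.)

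**Precision of strata.** Exact 95% intervals: 11/20 gives 32% to 77%; 5/10 gives 19% to 81%; 2/4 gives 7% to 93%. Stratum rates are very imprecise wherever the cut falls.

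**Power under a smooth effect.** From the documents: n = 20 and overall ORR 55% (the alternative). Assumed: two-sided 5%, a median split, and a logistic relation on evenly spaced VAF ranks,

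logit p(xᵢ) = a + b(xᵢ − 0.5), with xᵢ = (i − 0.5)/20 for i = 1,…,20,

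with a set so that the mean of p is 0.55, and b = 3, 4, 5, 6. These slopes are steep: response runs from 7–23% at the lowest VAF to 84–96% at the highest. Three tests were compared by simulation: Fisher's exact test on the split, mid-p Fisher on the split, and exact Wilcoxon on VAF between responders and non-responders.

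| Low half vs high half | Fisher, split | Mid-p, split | Wilcoxon, VAF | Wilcoxon − Fisher | Wilcoxon − mid-p |
|---|---|---|---|---|---|
| No effect | 1.4% | 4.3% | 4.6% | – | – |
| 38% vs 72% | 16% | 30% | 41% | 25 | 11 |
| 34% vs 76% | 28% | 47% | 62% | 34 | 15 |
| 30% vs 80% | 42% | 63% | 78% | 36 | 15 |
| 27% vs 83% | 55% | 76% | 89% | 34 | 13 |

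Across repeated runs the gaps were about 24 to 36 points for Fisher and about 10 to 16 for mid-p. The first row explains the difference. Fisher rejects only 1.4% of the time under no effect, so part of its shortfall is the conservatism of the test and not the cost of grouping. Mid-p has nearly the same size as Wilcoxon and isolates the cost of grouping.

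**Power under a step effect.** With the same half-cohort rates but a true step exactly at the cut, the mid-p split gives 30, 47, 63 and 74%, and Wilcoxon gives 25, 38, 52 and 61%. The split is ahead by 5, 9, 11 and 13 points. Plain Fisher trails Wilcoxon by 6 to 9 points.

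**Cross-check with another model.** With normally distributed VAF, odds ratios of 1.5 to 5 per SD, ORR 30% or 55%, and the likelihood-ratio test used both on measured VAF and on a median split, the loss was about 1 to 24 points. It shrinks as the slope flattens: at an odds ratio of 1.5, ORR 55% and two-sided 5%, power is 15.6% on measured VAF and 10.4% on the split, a loss of 5.2 points. Under a step at the cut the loss ran from about +2 to −6 points.

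**The case against.** The strongest reply is that Section 13.2 proposes estimation and not a test. Stratified rates in an exploratory analysis make no power claim, so there is no stated power to lose. Fisher's test is assigned in Section 13.8 to mutation combinations with a different outcome split (CR/CRp against PR or no response). Subclonality can also be read as a threshold idea, and under a true threshold the split does as well or better. Finally, several strata can show a non-monotone pattern, which a Wilcoxon test is not aimed at.

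Most of this stands. A reader might infer that the plan as written forfeits 24 to 36 points of power. The documents do not support that: the median split, the slopes and the use of Fisher for VAF are all assumptions, and much of that gap is Fisher's conservatism. A reader might also infer that a better VAF analysis would show whether ixazomib adds activity in subclonal disease. It would not: phase II is single-arm with no TAK-659-alone group. Nor do the documents show that a null comparison of strata would be reported as preserved activity.

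What the reply does not remove is that the threshold argument needs a threshold, and the plan names none. Nor does it explain why VAF has no model when Section 13.8 gives logistic regression to other markers.

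**Conclusion.** The point holds as a minor improvement to an exploratory analysis. Section 13.2 relies on VAF strata alone, in at most 20 patients, with no cut and no test. If response changes smoothly and steeply with VAF, grouping at the median costs about 10 to 16 points of power against an exact Wilcoxon test of similar size, and about 24 to 36 points if Fisher's test were used on the strata. Those ranges rest on the assumed slopes, 55% ORR, a median split and two-sided 5%. With flatter slopes the loss is smaller, and with a true step at the cut there is no loss from splitting. No stated figure in the plan is wrong on this point. Full-scale analysis would not make 20 patients informative about a modest VAF effect; it would use the data better and would not depend on where a cut is placed.

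**What to change.** In Sections 13.2 and 13.8:

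- Add an exploratory analysis of baseline FLT3 VAF on its full scale: an exact or Firth logistic regression giving response probability against VAF with a 95% CI, supported by an exact Wilcoxon comparison of VAF between responders and non-responders.
- Designate one baseline FLT3 assay and one specimen type for this analysis. Sections 3.1 and 8.3 allow several NGS laboratories and blood in place of marrow, so values may not otherwise be comparable.
- Keep the VAF-stratified rates as a descriptive table with exact CIs, using a subclonal cut that is justified and fixed before responses are reviewed.
- State that the analysis is exploratory and cannot isolate ixazomib's contribution.

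The cost is a few lines of text. No patients are added and the Simon design is unchanged. The downsides are that the added analysis assumes a one-direction relation between VAF and response, and that comparable VAF measurement across laboratories has to be arranged.
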